### 1.4 Interventions and Duration

Study participants in the treatment group will receive surface electrical stimulation intended to treat incontinence. Participants in the control group will receive non-therapeutic surface electrical stimulation. Treatment is self-administered in an at-home environment according to a defined schedule. Outcomes are assessed after 12 weeks.

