## 4.5 Retention Strategies

- Subjects who complete the study will be paid \$200 in cash or equivalent gift card. If the subject does not complete all study requirements the Clinical Director has discretion to compensate with a lesser amount.
- Subjects will be contacted after the 1st, 6th and 12th weeks to confirm ongoing participation and to provide the opportunity for subjects to ask questions.
- Subjects will have the option to download a mobile app that can keep track of progress of intensity level, days used, and leaks (if they enter it). This would not replace the diary.

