### 5.3 Description of Evaluations

This research utilizes validated methods for evaluating the clinical impact of the device/treatment, including several identified in the FDA guidance document regarding clinical studies that investigate urinary incontinence. Stress urinary incontinence episodes per day data, obtained from the subject's Daily Log, serves as the primary efficacy outcome measure (see 2.2). Analysis of adverse events serves as the primary safety outcome measure (see 2.2). Evaluations utilized throughout the study are described below. See 9.5 for detail regarding strategies for analyzing the data obtained in these evaluations.

- I-QoL Questionnaire (Pre- and Post-study) the Incontinence Quality of Life (I-QoL) questionnaire is validated tool for assessing changes in the degree to which urinary incontinence affects a woman's quality of life (TR-1131-FORM-2). It comprises 22 questions, to which the subject provides a numeric response on a 1-5 scale. The score is the sum of the numeric responses, which can range from 22 to 110. A change of 2.5 points is considered clinically significant. The I-QoL questionnaire is provided to the subjects as part of pre- and post-study materials. Completed questionnaires are returned to Elidah via mail or electronically (see 10.4).
- 24-Hour Pad Weight Test (Pre- and Post-study) This test is used to quantify the volume of urine leakage. The subject wears an absorbent pad(s) over a period of 24 hours, after which the pad(s) are weighed to determine the mass of any leaked urine. A reduction of ≥50% compared to a baseline measure is considered clinically significant. A mass of less than 1.3g is considered to be "dry", i.e. no leakage. Pre-weighed pads will be sent to the subjects as part of the study materials. During pre- and post-study assessments the subjects will wear the pad(s) for 24 hours, seal the pad(s) in a moisture proof bag, and mail to Elidah for weighing. Note that although this assessment does provide an objective

measure of change in leakage volume, the method is known to be subject to variability, may not be meaningful to patients, and requires subject compliance. For this reason, Elidah has identified this tool as a secondary outcome measure and does not intend to use the data as a primary means for establishing device efficacy.

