## 5.4 **Protocol Schedule**

The study comprises five stages: Pre-study, Baseline, Verification, Treatment, and Post-Study.

- **Pre-Study** –The subjects initiate pre-study activity, which includes completion of the I-QoL Questionnaire, the Pre-study Incontinence History and Usability Questionnaire, and the 24-hour pad weight test. The subject mails the pre-study materials back to Elidah. There is no difference in requirements between the two study arms.
- **Baseline** –Concurrently, the subjects maintain the Daily Log for 7 days to establish a baseline of the episodes/day and pads/day measures. No treatment is administered during this period. After 7 days the subjects submit the data to Elidah (electronically or hardcopy). Subjects are instructed that they should not perform baseline activity during menses or if they are ill. Note that it is acceptable to complete or return the pre-study materials throughout this 7 day baseline period. There is no difference in requirements between the two study arms.
- **Verification** If the 7 day baseline shows that the subject does not qualify based on urinary stress incontinence episodes, then the subject will be disqualified and the device will not be sent.
- Treatment Subjects will self-administer treatment with the Elitone device or a sham device according to their group assignment. The prescribed number of treatments starts at 5x/week and is reduced at points throughout the 12-week study duration. See Section 6 and Table 5-1 for a detailed description of the device and the treatment schedule. If subjects are ill or in menses during the twelfth study week they are instructed to extend treatment for at least 5 days after menses and/or they are in good health.
- Post-Study Upon completion of treatment subjects complete the post-study requirements, which include the I-QoL questionnaire, a 24-hour pad weight test, and a post-study usability

questionnaire. Subjects are requested to complete the requirements and return the study materials to Elidah within 3 days of completing treatment. There is no difference in post-study requirements between the two study arms.

 
Data used in primary and secondary endpoint analysis
 
Used to establish compliance.
 
	I-QoL Questionnaire	24-Hour Pad Weight Test	Pre-Study Usability Questionnaire	Number of Self- administered Treatment	Daily Log	Post-Study Usability Questionnaire	Adverse Events			
Pre-Study Data	•	•	•							
Baseline (Week 0)				0	•					

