## Table 5-1: Schedule of Study Activities/Requirements for Active and Control Groups.

### 5.5 Adherence Assessment

Adherence to the study regimen for the active group requires completion of  $\geq 60\%$  (18) of the treatment sessions prescribed during the first 6 weeks, as determined from review of each subject's Daily Log.

Elidah anticipates that subjects' willingness to continue with a frequent treatment schedule may diminish with time for reasons including:

- The subject achieves meaningful clinical improvement or complete elimination of incontinence symptoms during the early weeks of the study
- The subject believes she is in the control group
- The subject is not achieving clinical improvement and become discouraged with the likelihood of future improvement.

• Change in the subject's schedule and/or lifestyle

Accordingly, the prescribed treatment frequency over the latter half of the study is reduced (see Table 5-1). Correspondingly the minimum number of treatment sessions required for adherence is reduced to 1x/week for weeks 7-9 (33%) and 0x/week for weeks 10-12 (0%).

Further, subjects must complete the Pre-study, Baseline and Post-Study requirements to be considered compliant. If a subject does not adhere to the study requirements they will be asked to provide a reason, which will be documented in the Case Report Form (TR-1131-FORM-10). During data analysis, this information will be reviewed by the Data Safety and Monitoring Board to determine if/how the data should be adjudicated (see 10.5).

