## 8. INTERVENTION DISCONTINUATION

Subjects in the study have the right to discontinue treatment at any point during the study and for any reason. If the subject chooses to discontinue, a reason for discontinuation will be recorded and every effort will be made for the subject to complete the post-study activities defined in Table 5-1.

Elidah may wish to discontinue intervention for a subject for a variety of reasons including those listed below. Effort will be made to bring the subject into study compliance prior to terminating participation.

- Purposeful improper use of the device
- Failure to treat per the assigned schedule
- A recurring adverse event or unanticipated problem.
- Failure to maintain the Daily Log for greater than 2 weeks

A pause on enrollment and/or treatment of active subjects may occur if Elidah discovers a serious issue with the device/treatment (see 7.3). Elidah maintains the right to discontinue the study at any point and for any reason. Stopping treatment does not pose any risk to subjects. The study may be discontinued at any time by the IRB, FDA, or other regulatory or government agency as part of their duties to ensure that research participants are protected.

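### Section 8 does not secure the week-12 Daily Log once a woman stops treatment, so an earlier value can stand as her week-12 primary outcome

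*Combined protocol and SAP*

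**What the plan says.** **Outcome and timing.** Section 5.3 states: "Stress urinary incontinence episodes per day data, obtained from the subject's Daily Log, serves as the primary efficacy outcome measure". Section 1.4 states: "Outcomes are assessed after 12 weeks". Section 5.3 also obliges subjects to keep the log from the baseline week through week 12.

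**Stopping.** When the woman herself decides to stop, section 8 says that "every effort will be made for the subject to complete the post-study activities defined in Table 5-1". It then lists grounds on which the sponsor may discontinue her, and attaches no request for data to that case.

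**Post-study activities.** Section 5.4 gives their content, "which include the I-QoL questionnaire, a 24-hour pad weight test, and a post-study usability" questionnaire. The Post-Study row of Table 5-1 marks the same three items and adverse events, and its Daily Log cell is empty. On timing, section 5.4 asks subjects to complete them and "return the study materials to Elidah within 3 days of completing treatment".

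**Scoring and analysis set.** Section 9.5 defines the baseline and final weeks as the first and last five log entries, with no date limit. The primary test uses adherent subjects; an intent-to-treat analysis is permitted but not required.

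**Adherence.** Section 5.5 sets the 60% minimum (18 sessions in weeks 1-6) for the active group. The minimum then falls to one session a week in weeks 7-9 and none in weeks 10-12. To be compliant, a subject must also complete the pre-study, baseline and post-study requirements.

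**The concern.** The one clause about follow-up after stopping names the secondary measures and leaves out the primary one. Staff who follow section 8 and section 5.4 literally would collect an I-QoL score and a pad weight at the time of stopping and would not ask for a week-12 log. If the paper log goes back with the other materials, logging ends there.

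The last-five-entries rule then hides the gap. A log that ends early is not flagged as incomplete; its final entries are scored as the twelfth week. Section 5.5 itself expects use of the device to decline because of early improvement, belief of being on sham, or lack of benefit. Each is related to arm or to outcome, so the early values need not balance between arms. A log that was not kept cannot be recovered at analysis.

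**Working it through.** **Step 1. Does any section secure a week-12 log after stopping?**

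| Section | What it provides |
|---|---|
| 5.3 | General duty to log through week 12; silent on women who have stopped |
| 5.4 and Table 5-1, Post-Study | I-QoL, pad test, usability questionnaire (the table adds adverse events); no log; timed from end of treatment |
| 8, subject's decision | Post-study activities only |
| 8, sponsor's decision | No data request |
| 9.5 | Last five entries, undated |

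The duty in 5.3 is never withdrawn, but nothing says that it continues after stopping, and the specific clause points elsewhere.

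**Step 2. Who enters the primary analysis with an early value?**

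- *Active, stops before meeting the minimums for weeks 1-9:* not adherent, so outside the primary set. Only the optional intent-to-treat analysis is affected.
- *Active, stops after week 9:* no sessions are needed in weeks 10-12. If she does the post-study items she can count as adherent, and her last five entries may date from about week 9.
- *Sham, stops early:* the 60% minimum is stated for the active group only. If she does the post-study items she can count as compliant. The sentence on weeks 7-9 names no arm; if it binds sham women, those who stop before meeting it drop out of this group.

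The week-12 log sits in a treatment row of Table 5-1, so the compliance sentence in 5.5, which names the pre-study, baseline and post-study requirements, does not demand it.

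**Step 3. How many altered classifications matter?** With N women, R responders in total and n active women, the one-tailed Fisher p for a active responders is the sum over x ≥ a of C(n,x)·C(N−n,R−x)/C(N,R).

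- Plan's example, 24/40 v 5/20 (N=60, R=29, n=40, a=24): p=0.0105. This reproduces the 0.01 in 9.5.
- One more sham responder, 24/40 v 6/20 (R=30): p=0.027, above 0.025.

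**Step 4. All-randomised illustration.** Sections 5.2 and 9.1 allow 70-80 enrolled for 60 completers: 10/70=14% to 20/80=25% lost. I assume that the example describes the completers and that losses split about 2:1.

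| Enrolled | Lost, active/sham | All lost are non-responders | Same, but one lost sham woman responds |
|---|---|---|---|
| 70 | 7/3 | 24/47 v 5/23, p=0.017 | 24/47 v 6/23, p=0.041 |
| 75 | 10/5 | 24/50 v 5/25, p=0.016 | 24/50 v 6/25, p=0.038 |
| 80 | 13/7 | 24/53 v 5/27, p=0.016 | 24/53 v 6/27, p=0.037 |

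**The case against.** A reader might infer that the primary outcome of women who stop is never collected, or that they are asked for nothing but the post-study items. The documents do not support that. Section 5.3 requires the log of every subject through week 12. Section 8 gives a right to stop treatment without lifting that duty, and among the sponsor's grounds for discontinuation it lists lapsed logging separately from failure to treat. The last-five-entries rule also means that a returned early log gives a value, though from the wrong time. This stands, and it limits the point to data that are not secured or are misdated.

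It can also be said that completing treatment in 5.4 means finishing the 12-week stage: Table 5-1 still prescribes a weekly session in weeks 10-12, and 4.5 provides a contact after week 12. For a woman who keeps to the schedule that is the natural reading. For one who stops, section 8 sends her to the same items and gives no other clock.

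Third, the primary test is confined to adherent subjects, so active women who stop early are excluded with or without a log. That stands for them, but not for the two groups identified in the working.

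Last, the 10-20 losses do not estimate this problem. Section 5.2 attributes them to women who fail to complete treatment and return materials, and rewording section 8 will not recover women who return nothing. Assignment takes place at consent (9.2), before baseline verification (5.4), so some of the 70-80 may never receive a device. This stands too: the Step 4 figures would apply to any loss of that size in an analysis that the plan makes optional.

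**Conclusion.** The point holds as an unresolved tension with a route into the primary result. Section 8 does not secure the week-12 log after treatment stops, and 9.5 lets earlier entries take its place. The primary analysis is exposed through active women who stop after week 9 and through sham women, for whom no 60% minimum is stated; for active women who stop earlier, the effect is confined to the intent-to-treat analysis.

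The size is illustrative, because the documents do not say how many women stop the device yet remain reachable, or in which direction an early value would err. In the plan's own example a single reclassified sham woman moves p from 0.0105 to 0.027. In the all-randomised illustration, one lost sham woman counted as a responder moves p from 0.016-0.017 to 0.037-0.041. Both rest on the example's responder counts, and the second also on 10-20 losses split about 2:1.

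This should be fixed before enrolment. It is not a demonstrated failure of the primary analysis.

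Payment is not part of the error. Section 4.5 says "If the subject does not complete all study requirements the Clinical Director has discretion to compensate with a lesser amount", which does not expressly tie the $200 to device use; a weaker incentive to keep logging is an inference.

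**What to change.** Reconcile sections 5.3, 5.4, 8 and 9.5. The changes concern data collection only.

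- **Section 8:** state that any subject in either arm who stops the device, by her own or the sponsor's decision, is asked to keep the Daily Log through study week 12, counted from treatment start, and to do the I-QoL and pad test then.
- **Section 5.4:** time the post-study items from the end of study week 12, or of the week-13 extension where it applies.
- **Section 9.5:** require the final five entries to fall in the week-12/13 window, so that an early-ending log shows as missing.

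Linking payment in 4.5 to return of the data is optional.

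The cost is protocol wording and a few more logs to chase. The log, pads and prepaid postage are already supplied (10.1, 10.2), and the contact after week 12 already exists (4.5).

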### 9.5 Data Analyses

Analysis of the **primary efficacy endpoint** will proceed as follows. Each adherent subject's Daily Log will be used to determine the average number of SUI episodes per day for the baseline and  $12^{th}$  weeks (see 5.5 regarding subject adherence). To accommodate the likelihood that some subjects will omit log data, the "weeks" referred to in the baseline and 12th week assessments refer to the first and last 5 entries in the Daily Log. The percent reduction in SUI episodes is then calculated by subtracting the final week average from the baseline average, dividing the difference by the baseline average, and multiplying by 100. Subjects with a percent reduction of  $\geq$ 50% are considered responders. The number of responders from each group is then compared using a one-tailed Fisher's exact test for groups of unequal size, and p $\leq$ 0.025. For example, if 24 of 40 subjects (60%) from the active group responded and 5 of 20 (25%) from the control group responded, the active treatment would be considered effective (p=0.01).

SUI episodes per day data can additionally be characterized simply in terms of percent reduction (independent of whether it reaches a 50% level of clinical significance) and the treatment groups analyzed using a 2 sample t-test with unequal group sizes. This approach is commonly reported in the literature. This value may additionally be reported but is not intended for use in determining whether the study met its endpoint. This use of a secondary analysis method on a single endpoint after success of the primary analysis method is generally understood to not inflate the Type 1 error rate, so no multiplicity adjustments are necessary.

Also note that confidence intervals and associated effect size calculations may also be made on the same data, but no multiplicity adjustments are warranted. Similarly, the data may be additionally analyzed using intent-to-treat criteria instead of with per-protocol criteria as defined in 5.5.

Regarding **secondary outcome measures**, three tests are prospectively defined with the intent of using the results to support future product labeling and marketing. The Hochberg procedure

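### Section 8 allows the sponsor to end participation for missed sessions or log gaps that 5.5 and 9.5 can accept, and the plan does not provide for collecting week-12 outcome after such a stop

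*Combined protocol and SAP*

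**What the plan says.** **Section 8 (Intervention Discontinuation).** The sponsor's power is permissive: "Elidah may wish to discontinue intervention for a subject for a variety of reasons including those listed below". The list includes "Failure to treat per the assigned schedule", with no number attached, and "Failure to maintain the Daily Log for greater than 2 weeks". Before it is used, "Effort will be made to bring the subject into study compliance prior to terminating participation". The paragraph thus begins with stopping the intervention and ends with stopping participation. Follow-up is promised in the preceding paragraph, about a subject's own decision to stop: "If the subject chooses to discontinue, a reason for discontinuation will be recorded and every effort will be made" to have her complete the post-study activities of Table 5-1. No matching sentence covers a stop made by the sponsor.

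**Table 5-1 and section 5.4.** Five sessions a week are prescribed in weeks 1-6, three in weeks 7-9 and one in weeks 10-12. The post-study row covers I-QoL, the pad weight test, the usability questionnaire and adverse events. It does not include the Daily Log.

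**Section 5.5.** Adherence in the active group requires at least 60% (18) of the sessions in weeks 1-6, then one a week in weeks 7-9 and none in weeks 10-12. A compliant subject must also complete the pre-study, baseline and post-study requirements. Non-adherent subjects are asked why, and the monitoring board decides how their data are handled.

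**Section 9.5.** The primary analysis uses adherent subjects. It expects omitted log data and defines the baseline and final weeks as "the first and last 5 entries in the Daily Log". Intent-to-treat analysis is optional.

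**The concern.** Sections 5.5 and 8 measure the same behaviour by different standards. A subject can meet the analysis definition of adherence and still satisfy, read literally, a ground for termination. If she is terminated before the post-study stage, she can no longer be compliant under 5.5 and drops out of the primary set because of a decision taken after randomization. The plan makes no provision for collecting her week-12 data, so the optional intent-to-treat analysis is weakened as well.

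The loss is unlikely to be random. Section 5.5 itself expects women who are not improving, women who have already improved and women who believe they are on sham to treat less. Section 9.3 accepts that staff in contact with subjects may learn the assignment from their remarks. A discretionary rule without a threshold then leaves room for exclusions linked to outcome, without any bad intent.

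**Working it through.** **1. Sessions prescribed and sessions required** (Table 5-1 and 5.5; the as-needed week 13 is left out).
- Weeks 1-6: 6 × 5 = 30. The 60% rule gives 0.60 × 30 = 18, which reproduces the plan's own figure.
- Prescribed total: 30 + (3 × 3) + (3 × 1) = 42.
- Minimum for adherence: 18 + (3 × 1) + 0 = 21, and 21/42 = 50%.
- A subject may miss 42 − 21 = 21 sessions and remain adherent under 5.5, whereas section 8 sets no number that separates an acceptable miss from a failure to follow the schedule. The 18-session minimum is stated for the active group only; section 8 applies to both arms.

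**2. Log gaps of more than 2 weeks.** Every possible start day of a single gap in an 84-day log was enumerated. Assumptions: sessions fall on days 1-5 of weeks 1-6, days 1, 3 and 5 of weeks 7-9, and day 1 of weeks 10-12; all other sessions are done; a session counts only if logged.

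| Gap length | Start days | Meets 5.5 session minimums | Also leaves ≥5 entries in week 12 |
|---|---|---|---|
| 15 days | 70 | 45 | 40 |
| 21 days | 64 | 9 | 4 |

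A 15-day gap wholly inside weeks 1-6 always leaves at least 18 logged sessions. A gap that blanks week 7, 8 or 9 fails the once-a-week minimum. So some gaps over 2 weeks are compatible with 5.5 and 9.5, but not all.

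**3. What happens to the outcome data.**

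| | Subject chooses to stop | Sponsor stops the subject |
|---|---|---|
| Post-study activities | Every effort promised (section 8) | Not addressed |
| Daily Log to week 12 | Not named | Not addressed |
| Primary set | Out unless 5.5 is met, including post-study | Out if stopped before post-study |
| Optional intent-to-treat value | At best, last 5 entries before stopping, unless she keeps logging | Same |

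The rule on the last five entries carries no date limit, so a returned log can still yield a value. That value describes her state when she stopped, not at week 12.

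**4. Sensitivity of the primary test** (one-tailed Fisher's exact, criterion p≤0.025 from 9.5). The plan's example, 24/40 v 5/20, gives p=0.0105, against the stated 0.01. Near the boundary:

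| Active | Control | p | Criterion |
|---|---|---|---|
| 22/40 | 5/20 | 0.0258 | not met |
| 22/39 (one active non-responder removed) | 5/20 | 0.0208 | met |
| 22/40 | 5/19 (one control non-responder removed) | 0.0358 | not met |
| 22/39 | 5/19 (one from each arm) | 0.0292 | not met |

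These tables were chosen to sit near the boundary. They show how thin the margin can be and that the shift can go either way.

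**5. Room for loss.** Sections 5.2 and 9.1 expect 70-80 subjects to yield 60, a loss of 10/70 = 14.3% to 20/80 = 25%. The plan does not divide this by reason.

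**The case against.** The best defence is that an operational ground for stopping and an analysis threshold serve different purposes and need not share a number. The sponsor's power is optional and is preceded by an effort to restore compliance, a word that 5.5 also uses. Opportunity is limited too: the hardcopy log comes back at the end of the study and scheduled contacts fall after weeks 1, 6 and 12, so many lapses would surface too late to act on. The log also documents adherence and can reveal adverse events, so a limit on gaps has a purpose beyond 9.5. All of this stands. It lowers the likely frequency, but it neither supplies the missing threshold nor the missing follow-up sentence.

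Four stronger readings are tempting and are not supported:
- *That removal is automatic.* Section 8 is permissive.
- *That outcome data from a sponsor-stopped subject are barred or irrecoverable.* The plan is silent; nothing forbids collection, and the undated rule on the last five entries could still give a value.
- *That subjects who stop by choice are fully followed to the primary outcome.* Their promise covers the post-study activities, and the Daily Log is not among them.
- *That removals would favour the device, or that a single one would decide the trial.* The direction is unknown, since women who believe they are on sham may also lapse. A subject who is already non-adherent under 5.5 would leave the per-protocol set without section 8. The 40 and 20 targets already allow for dropout, so one removal need not leave 39.

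The monitoring board's review of non-adherent subjects is a real safeguard for handling data in hand. It cannot restore data that were never collected.

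**Conclusion.** The point holds as a gap between sections 8, 5.5 and 9.5 and as an omission in follow-up, not as a flat contradiction or a demonstrated bias. An active subject with between 21 and 41 of the 42 sessions, distributed as 5.5 requires, can meet the session minimums and still come within section 8's wording; so can some subjects with a log gap of more than 2 weeks. If such a subject is terminated before post-study, she leaves the primary set and nothing in the plan secures her week-12 outcome.

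The number affected cannot be estimated, because the documents give no removal rate. The p-values show sensitivity at a chosen boundary and are not a forecast. The gap counts rest on the assumed session days. The change is worth making because the loss is avoidable and may be linked to outcome in a trial of 60 analysed subjects.

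**What to change.** 1. Reconcile the treatment and log criteria in section 8 with 5.5 and 9.5, and state how they relate in each arm. No view is taken here on which should prevail.
2. In section 8, distinguish ending device use from ending participation in the study.
3. Extend the sentence promising that "every effort will be made for the subject to complete the post-study activities defined in Table 5-1" to every subject whose device use ends, whoever decides, unless she withdraws consent. Name the Daily Log to week 12 alongside the post-study activities, since it supplies the primary endpoint.

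The cost is wording in section 8, plus continued contact and mailing for a few subjects who no longer use the device. The sample size and the primary test are unaffected.
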